9.4.3 Correlative Study Calendar

Correlative Study	Blood/Tumor	Type of Collection	Volume	Time Point	Process at Site	Temperature conditions for storage/shipping
Archival tumor for research	Primary tumor	Tumor rich block (preferred) or 15-20 10 micron section unstained slides. H&E slide needed as well	N/A	Baseline	N/A	Ambient
Archival tumor for research	Metastatic tumor	Tumor rich block (preferred) or 15-20 10 micron section unstained slides. H&E slide needed as well	N/A	Baseline	N/A	Ambient
Tumor for research (optional)	Tumor	1 core processed into paraffin embedded block, 2 cores frozen in OCT at bedside, 2 cores in DMEM fresh (Wash U patients only)	3 cores secondary sites, 5 cores Wash U only	Baseline and at Time of Disease Progression	NO	Core #1 should be processed into a paraffin embedded block and be stored/shipped at ambient temperature (batch shipments for secondary sites). Cores #2 and #4 should be immediately snap frozen and stored at -60 °C to -80°C (batch shipments for secondary sites). Cores #3 and #5 placed in cold DMEM Glucose media should be chilled on wet ice and immediately taken to [name] lab (Wash U only)
Serum for research	Whole blood	Clot tube (red)	4-5 mL	Baseline, C1D15, C2D1, every 2-3 months thereafter (to coincide with imaging), time of progression	YES	Stored at -60°C to -80°C (secondary sites will ship in batches)

Plasma for research	Whole blood	EDTA (pink or purple) – the baseline EDTA tube collected for plasma will also be processed for germline DNA	8 mL	Baseline, C1D15, C2D1, every 2-3 months thereafter (to coincide with imaging), time of progression	YES	Stored at -60°C to -80°C (secondary sites will ship in batches)
Whole blood for plasma circulating DNA (ctDNA)	Whole blood	Cell-free DNA BCT (Streck)	8 mL x 2	Baseline, C1D15, C2D1, every 2-3 months thereafter (to coincide with imaging), time of progression	YES	Stored at -60°C to -80°C (secondary sites will ship in batches)
Germline DNA for research	Whole blood	EDTA (pink or purple) – the baseline EDTA tube collected for plasma will also be processed for germline DNA	8 mL	Baseline	YES	Stored at -60°C to -80°C (secondary sites will ship in batches)
Blood for detection of circulating tumor cells	Whole blood	ACD (yellow)	8 mL	Baseline, C2D1, post 2-3 months after start of therapy (coincide with ONLY 1 st imaging), time of progression	YES	Shipped overnight to UCLA on ice (avoid Fridays and day before holiday)
Blood for detection of circulating tumor cells (Wash U ONLY)	Whole blood	EDTA (purple)	8 mL	Baseline, C2D1, post 2-3 months after start of therapy (coincide with ONLY 1 st imaging), time of progression	YES	Transported on ice (after mixing) to [name] lab

10.0 STUDY CALENDAR

Screening/baseline evaluations are to be conducted within 2 weeks prior to start of protocol therapy. Scans and x-rays must be done no more than 4 weeks prior to the start of the protocol therapy. There is a +/-3 day window around each study visit.

	Screening	Baseline	Day 1 of each cycle ⁸	C1D15	C2D1	C2D15	End of every 2 nd or 3 rd cycle ⁸	Time of progression	30 day f/u
Informed consent	X								
H&P, ECOG PS	X		X		X			X	
CBC w/diff	X		X	X	X	X			
CMP	X		X		X				
β-hCG ¹	X								
Imaging	X						X	X	
Palbociclib			Given on a 5 days on / 2 days off schedule for each 28-day cycle						
Fulvestrant ³			X	X	X				
Letrozole ³			Daily						
Goserelin ⁴			X		X				
Medication diary			Daily, to be returned at the end of each cycle						
AE assessment			X -----X						
Archival Tissue		X ⁷							
Research biopsy (optional)		X						X	
Blood for serum		X		X ⁵	X ⁵		X ^{2,5}	X	
Blood for plasma		X		X ⁵	X ⁵		X ^{2,5}	X	
Blood for cfDNA		X		X ⁵	X ⁵		X ^{2,5}	X	
Blood for germline DNA		X							
Blood for circulating tumor cells		X			X		X ⁶	X	

1. Women of childbearing potential only
2. Beginning with the end of Cycle 2 but to coincide with imaging studies
3. Either fulvestrant OR letrozole will be given (MD decision)
4. Goserelin will be given to premenopausal women only
5. Instruct patient take palbociclib/hormonal therapy after blood draw, meaning blood draw needs to happen prior to the day's treatment.
6. Post 2 or 3 months after start of therapy (to coincide with ONLY the 1st imaging assessment of tumor response)
7. Archival tissue should include both primary and metastatic tissue
8. Labs and office visits could be reduced in frequency to q2-3 cycles to coincide with tumor imaging studies in patients on stable doses of palbociclib for at least 6 consecutive cycle

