1.3 Study Rationale

The current dose modification guidelines for palbociclib are as follows:

CTCAE* grade	Dose modifications
Grade 1 or 2	No adjustment required
Grade 3	No dose adjustment is required. Consider repeating complete blood count monitoring one week later. Withhold initiation of next cycle until recovery to Grade ≤ 2
Grade 3 ANC (<1000 to 500/mm ³) + Fever ≥ 38.5 C and/or infection	Withhold Palbociclib and initiation of next cycle until recovery to Grade ≤ 2 (≥ 1000 /mm ³). Resume at next lower dose
Grade 4	Withhold Palbociclib and initiation of next cycle until recovery to Grade ≤ 2 . Resume at next lower dose

*Common terminology criteria for adverse events

We propose to conduct a study to test an alternative dosing schedule of palbociclib. With the current three-week on and one week off schedule, a significant number of patients develop grade 3 or higher degree of neutropenia and require dose reduction and sometimes discontinuation. This potentially compromises the efficacy of the drug. In addition, as the half-life of palbociclib is 27 hours, 1 week break with the standard 3 weeks on and 1 week off dosing schedule could potentially lead to recovery of Rb phosphorylation during the off week. Hence, we propose a 5 days on and 2 days off schedule each week without any weeks off drug. Although the cumulative doses each 28-day cycle is roughly the same with this schedule compared to conventional dosing, the bone marrow is not exposed to the drug continuously for 21 days and rather gets frequent breaks from therapy. We hypothesize that the 5 days on and 2 days off schedule is more tolerable with less frequent high grade neutropenia and dose interruption/reduction. In addition, this schedule also provides for a more continuous drug delivery to the patient since there is not a week's break in therapy, which could ultimately prove to be more efficacious.

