1.4 Correlative Studies Background

Serum TK1 activity

Thymidine kinase-1 (TK1) is an enzyme which plays a critical role in the synthesis of DNA. All human cells express this enzyme during normal cell division through E2F-dependent transcription with only small amounts of the enzyme released into the serum (14,15). Due to higher rates of replication compared to normal tissues, tumors are capable of secreting pathologic levels of TK1 which can be detected via an ELISA assay. In patients with metastatic breast cancer, TK1 expression and activity in human serum, was predictive for therapy response and correlated with PFS and OS (16). Given that TK1 expression is E2F-dependent, we hypothesize that CDK4 inhibitors, if active in a particular tumor, would result in reduced serum TK1 activity and can be used as a potential biomarker

for the pharmacodynamics effect of CDK4/6 inhibition. We will also evaluate changes in serum TK1 activity in relation to tumor response as an exploratory endpoint in this study.

Cell-free circulating tumor DNA (ctDNA) sequencing

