2.3 Exploratory Objectives

1. To assess changes in cell free DNA mutation profile, including mutations in TP53, PIK3CA, ESR1, and RB1 and their correlation with treatment response.
2. To correlate archival tumor mutation profile and RB protein status with treatment response.
3. To assess intrinsic and acquired resistance mechanisms to palbociclib in tumor samples collected at baseline and at progression.
4. To assess changes in serum thymidine kinase activity and correlate with treatment response and absolute neutrophil count.
5. To establish patient derived xenograft (PDX) models from tumor biopsies before treatment and at progression for future studies.
6. To assess baseline and changes in Circulating Tumor Cell (CTC) gene expression profiles and to correlate with treatment response.

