5.0 TREATMENT PLAN

5.1 Agent Administration

Agent	Dose	Route	Schedule	Cycle Length
Palbociclib	125 mg	PO	5 days on and 2 days off, starting C1D1	28 days (4 weeks)
Letrozole*	2.5 mg	PO	Daily	
Fulvestrant*	500 mg	IM	Every 14 days for the first 3 doses followed by every 28 days	
Goserelin**	3.6 mg	SC	Every 28 days (Day 1 of each cycle)	
* Letrozole OR fulvestrant will be administered with palbociclib per physician choice. ** Only if pre- or peri-menopausal				

Patients will be instructed to make use of medication diaries (Appendices B and C) to act as records of administration for palbociclib and letrozole (if applicable).

Palbociclib at a dose of 125 mg should be taken by mouth with food on a 5 days on/2 days off schedule (meaning: on Days 1-5, 8-12, 15-19, and 22-26 of each 28-day cycle). If a patient misses a day's dose entirely, she must be instructed not to make it up the next day but just take her regular dose at the next assigned time. If a patient vomits any time after taking a dose, she must be instructed not to retake the dose but resume subsequent dosing at the next assigned time. If a patient inadvertently takes an extra dose during a day, she must be instructed to not take the next day's dose.

Patients who have been on stable doses of palbociclib for 6 consecutive cycles can be assessed for retreatment every 2 or 3 cycles to coincide with imaging. These patients must meet retreatment criteria (as described in Section 6.4) and will have labs drawn for retreatment (CBC with differential and CMP) and correlative studies (serum, plasma, cell-free DNA, and circulating tumor cells) to correspond with imaging studies that take place every 2-3 cycles. This allows patients on stable doses of palbociclib to return to clinic for retreatment at greater intervals.

Patients who are receiving letrozole will take it daily by mouth, every day of each 28-day cycle, at a dose of 2.5 mg. If a patient misses a day's dose entirely, she must be instructed not to make it up the next day but just take her regular dose on the next day. If a patient vomits any time after taking a dose, she must be instructed not to retake the dose but resume subsequent dosing on the next day. If a patient inadvertently takes an extra dose during a day, she must be instructed to not take the next day's dose.

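### The nominal C1D15 and C2D1 serum TK1 samples are post-break trough samples, and the TK1 analysis in 15.3 ignores time since the last palbociclib dose

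*Combined protocol and SAP*

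**What the plan says.** Section 5.1 schedules palbociclib "on Days 1-5, 8-12, 15-19, and 22-26 of each 28-day cycle", which leaves Days 6-7, 13-14, 20-21 and 27-28 without drug. The correlative study calendar (9.4.3) lists the serum time points as "Baseline, C1D15, C2D1, every 2-3 months thereafter (to coincide with imaging), time of progression". Footnote 5 in section 10.0 is attached to the C1D15, C2D1 and imaging draws and reads "Instruct patient take palbociclib/hormonal therapy after blood draw, meaning blood draw needs to happen prior to the day's treatment". The same section adds: "There is a +/-3 day window around each study visit".

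Section 1.4 gives the purpose. It expects that an active CDK4 inhibitor "would result in reduced serum TK1 activity and can be used as a potential biomarker" "for the pharmacodynamics effect of CDK4/6 inhibition". Exploratory objective 4 in section 2.3 is "To assess changes in serum thymidine kinase activity and correlate with treatment response and absolute neutrophil count". Section 15.3 plans Pearson or Spearman coefficients of TK1 with ANC and with tumor response. It has no term for when in the dosing week the blood was taken.

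Section 1.3 argues that, "as the half-life of palbociclib is 27 hours", Rb phosphorylation might recover during the one-week break of the standard schedule. It makes no such statement about the two-day break.

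**The concern.** A marker of drug effect is easiest to interpret when every sample has a known and similar relation to dosing. Here the two nominal early on-treatment samples sit at the lowest drug level of the week, and nothing in the plan says so. If TK1 falls only a little from baseline, the result could mean weak inhibition, or good inhibition with partial recovery over the break. The planned analysis could not separate the two.

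The second difficulty is spread. Under the visit window, tubes with the same visit label can come from different points of the dosing week, which adds noise to the TK1 correlations. It may add bias as well. Section 6.4 makes dose interruption and cycle delay depend on ANC, so time off drug can be related to the very variable with which TK1 is to be correlated. The scheduled blood counts in Cycle 1 are on Days 1 and 15, so this route mainly concerns C2D1 and later draws.

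**Working it through.** The plan gives no sample size, expected drug level or expected change for TK1, so it has no figure of its own to reproduce. The inputs are the dosing days (5.1), the draw days and pre-dose rule (9.4.3 and 10.0), the ±3-day window (10.0) and the 27-hour half-life (1.3). First-order elimination with equal doses added together is an assumption. So is the alternative half-life range of 20 to 34 hours.

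**1. Time since last dose on the nominal days.** C1D15: Day 15 − Day 12 = 3 days = 72 h. C2D1 (Day 29): Day 29 − Day 26 = 3 days = 72 h.

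**2. Relative pre-dose level.** For day D, L(D) = sum of 2^(−24(D − d)/27) over all dosing days d before D. One day's decay is r = 2^(−24/27) = 0.540.

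- Day 12: doses on Days 8-11 give 0.540 + 0.292 + 0.157 + 0.085 = 1.074. Days 1-5 add 0.028. L = 1.102.
- Day 15: doses on Days 8-12 give 0.013 + 0.025 + 0.046 + 0.085 + 0.157 = 0.327 (before rounding of the terms). Days 1-5 add 0.004. L = 0.331.
- Ratio: 0.331 / 1.102 = 0.30. Day 29 against Day 26 gives the same 0.30.
- Half-life 20 h: 0.144 / 0.748 = 0.19. Half-life 34 h: 0.562 / 1.437 = 0.39.
- Against the trough under uninterrupted daily dosing, r/(1 − r) = 1.174: 0.331 / 1.174 = 0.28.

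**3. Spread inside the window** around C1D15, with dosing kept on the nominal calendar and a 27 h half-life:

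| Draw day | Hours since last capsule | L | L relative to Day 12 |
|---|---|---|---|
| 12 | 24 | 1.10 | 1.00 |
| 13 | 24 | 1.14 | 1.03 |
| 14 | 48 | 0.61 | 0.56 |
| 15 | 72 | 0.33 | 0.30 |
| 16 | 24 | 0.72 | 0.65 |
| 17 | 24 | 0.93 | 0.84 |
| 18 | 24 | 1.04 | 0.94 |

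The largest to smallest ratio is 1.135 / 0.331 = 3.4, with the minimum on the nominal day. Days 26 to 32 around C2D1 give the same pattern if Cycle 2 dosing starts on Day 29. The imaging draws have no set place in the dosing week; a visit at the true end of a cycle falls on off-Day 27 or 28, that is 24 or 48 h after the last capsule.

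**4. Holds and delays.** Under section 6.4 palbociclib is interrupted within a cycle for ANC below 500/mcL, and a new cycle needs at least 1,000/mcL, failing which it is delayed by one week. If the C2D1 draw moves with a one-week delay, the gap becomes 72 + 168 = 240 h.

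**5. Is drug still present at 72 h?** Mean Day 8 Cmax at 125 mg is 86.2 ng/mL (8.1.3) and the molecular weight is 447.5 (8.1.1), so 86.2 / 447.5 × 1000 = 193 nM. Median Tmax is 4 h, which leaves 72 − 4 = 68 h of decay: 193 × 2^(−68/27) = about 34 nM (18 nM at a half-life of 20 h, 48 nM at 34 h). Section 8.1.2 quotes an IC50 of 11 nM for CDK4. The first figure is total drug and the second a kinase inhibition value, so the comparison is only rough.

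**The case against.** The strongest defense is that trough sampling is a legitimate choice. The new schedule is meant to avoid the long break, and a sample taken after the short break tests whether suppression lasts through it. Day 15 and Day 1 are also dosing days; what makes the samples troughs is the two off-days before them. This stands, and it is why the point is not that the draw days are wrong. But the plan does not describe the samples as troughs, and the visit window means they are not consistently so.

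A reader might infer that TK1 is measured without CDK4/6 inhibition. The documents do not support that. Some 28% to 30% of the pre-dose level remains under the simple model, and the rough residual of 34 nM lies above the only potency figure given. That does not prove inhibition, but it bars asserting its absence. Nor can section 1.3 be used to claim recovery here, since it speaks of seven days off and not two.

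It is also fair to say that the 3.4-fold spread is in modelled drug level and not in TK1. The documents give no TK1 recovery time or concentration-effect relation, so the effect on the correlations could be large or negligible.

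Moving the C1D15 serum draw to later in a dosing block may look like the obvious remedy. It would separate serum from the CBC taken at the same visit, which the TK1-ANC correlation needs. Moving the CBC as well would change the timing of counts that feed the primary neutropenia endpoint. That cost is not justified for an exploratory marker.

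**Conclusion.** The concern holds in limited form. On the nominal calendar, the C1D15 and C2D1 TK1 samples are pre-dose, post-break trough samples, 72 h after the last scheduled capsule. The drug level is then about 30% of that before the Day 12 or Day 26 dose (19% to 39% over the assumed half-lives). They may understate TK1 suppression on drug. By how much cannot be stated from the documents.

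Time since last dose can range from 24 to 72 h under one visit label, and longer after a hold or delayed cycle. The planned correlations do not account for this. The 72 h figure is calendar arithmetic and needs no model; the percentages rest on first-order elimination and full adherence to the schedule.

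Severity is minor. Only exploratory objective 4 is affected, no decision rule depends on TK1, and the primary neutropenia test is untouched.

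**What to change.** Leave dosing, draw days and the same-visit pairing of serum with CBC unchanged.

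1. In sections 9.3 and 10.0, state that the nominal C1D15 and C2D1 samples are post-break trough samples.
2. Record the date and clock time of each serum draw, for example on the Specimen Collection Form listed in section 11.0.
3. Derive hours since last palbociclib dose for every sample, using the dose dates and times already entered in the Appendix B diary.
4. In section 15.3, analyse TK1 change and its correlations with ANC and response adjusted for hours since last dose, by partial correlation or as a model covariate. Add a sensitivity analysis restricted to samples from the same dosing phase.

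The cost is small: draw time must be captured, and one parameter is added to a small exploratory analysis. The restricted analysis will lose some samples, and the derived variable is only as good as the diary entries. No extra tube or visit is needed, and samples already taken can be included where the draw time can be recovered.

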11.0 DATA SUBMISSION SCHEDULE

Case report forms with appropriate source documentation will be completed according to the schedule listed in this section.

Case Report Form	Submission Schedule
Original Consent Form	Prior to registration
On-Study Form	Prior to starting treatment
Treatment Form	Every cycle ¹ and end of treatment
Toxicity Form	Continuous
Treatment Summary Form	Completion of treatment
Specimen Collection Form	Per protocol
Follow Up Form	30 Day follow-up
Tumor Measurement Form	Baseline, end of every 2 nd or 3 rd cycle, and end of treatment

¹At physician discretion, patients that have been on a stable dose of Palbo for 6 consecutive cycles, may dose in q2-3 cycle intervals to coincide with tumor imaging studies. The treatment data forms will be completed accordingly.

Any queries generated by Washington University must be responded to within 28 days of receipt by the participating site. The Washington University research team will conduct a regular review of data status at all secondary sites, with appropriate corrective action to be requested as needed.

12.0 MEASUREMENT OF EFFECT

12.1 Antitumor Effect – Solid Tumors

For the purposes of this study, patients should be re-evaluated for response every 12 weeks. In addition to a baseline scan, confirmatory scans should also be obtained not less than 4 weeks following initial documentation of objective response.

Response and progression will be evaluated in this study using the new international criteria proposed by the revised Response Evaluation Criteria in Solid Tumors (RECIST) guideline (version 1.1) (34). Changes in the largest diameter (unidimensional measurement) of the tumor lesions and the shortest diameter in the case of malignant lymph nodes are used in the RECIST criteria.

12.2 Disease Parameters

Measurable disease: Measurable lesions are defined as those that can be accurately measured in at least one dimension (longest diameter to be recorded) as >20 mm by chest x-ray, as >10 mm with CT scan, or >10 mm with calipers by clinical exam. All tumor measurements must be recorded in millimeters (or decimal fractions of centimeters).

Malignant lymph nodes: To be considered pathologically enlarged and measurable, a lymph node must be >15 mm in short axis when assessed by CT scan (CT scan slice thickness recommended to be no greater than 5 mm). At baseline and in follow-up, only the short axis will be measured and followed.

Non-measurable disease: All other lesions (or sites of disease), including small lesions (longest diameter <10 mm or pathological lymph nodes with ≥ 10 to <15 mm short axis), are considered non-measurable disease. Bone lesions, leptomeningeal disease, ascites, pleural/pericardial effusions, lymphangitis cutis/pulmonitis, inflammatory breast disease, and abdominal masses (not followed by CT or MRI), are considered as non-measurable.

Note: Cystic lesions that meet the criteria for radiographically defined simple cysts should not be considered as malignant lesions (neither measurable nor non-measurable) since they are, by definition, simple cysts.

‘Cystic lesions’ thought to represent cystic metastases can be considered as measurable lesions, if they meet the definition of measurability described above. However, if non-cystic lesions are present in the same patient, these are preferred for selection as target lesions.

Target lesions: All measurable lesions up to a maximum of 2 lesions per organ and 5 lesions in total, representative of all involved organs, should be identified as target lesions and recorded and measured at baseline. Target lesions should be selected on the basis of their size (lesions with the longest diameter), be representative of all involved organs, but in addition should be those that lend themselves to reproducible repeated measurements. It may be the case that, on occasion, the largest lesion does not lend itself to reproducible measurement in which circumstance the next largest lesion which can be measured reproducibly should be selected. A sum of the diameters (longest for non-nodal lesions, short axis for nodal lesions) for all target lesions will be calculated and reported as the baseline sum diameters. If lymph nodes are to be included in the sum, then only the short axis is added into the sum. The baseline sum diameters will be used as reference to further characterize any objective tumor regression in the measurable dimension of the disease.

Non-target lesions: All other lesions (or sites of disease) including any measurable lesions over and above the 5 target lesions should be identified as non-target lesions and should also be recorded at baseline. Measurements of these lesions are not required, but the presence, absence, or in rare cases unequivocal progression of each should be noted throughout follow-up.

